2. INTRODUCTION

PF-07321332, a potent and selective SARS-CoV-2 3CL protease inhibitor, is being investigated as an oral antiviral treatment of COVID-19.

The purpose of this study is to evaluate the efficacy and safety of PF-07321332/ritonavir for the treatment of nonhospitalized, symptomatic adult participants with COVID-19 who are at increased risk of progressing to severe illness.

2.1. Study Objectives, Endpoints, and Estimands

Primary Efficacy Objective: To compare the efficacy of PF-07321332/ritonavir to placebo for the treatment of COVID-19 in nonhospitalized symptomatic adult participants with COVID-19 who are at increased risk of progression to severe disease.

PFIZER CONFIDENTIAL
Page 11

Secondary Efficacy Objective: To compare PF-07321332/ritonavir to placebo for the duration and severity of signs and symptoms in nonhospitalized symptomatic adult participants with COVID-19 who are at increased risk of progression to severe disease.

Secondary Safety Objective: To describe the safety and tolerability of *PF-07321332/ritonavir relative to placebo in the treatment of nonhospitalized symptomatic adult participants with COVID-19 who are at increased risk of progression to severe disease.*

2.1.1. Primary Estimand

The difference in proportions of patients experiencing COVID19 related hospitalization or death from any cause through Day 28 in nonhospitalized adult patients with symptomatic COVID-19 who are at increased risk of progression to severe disease (as defined in Section 5.1 in Protocol) who did not receive COVID-19 therapeutic mAb treatment, and were treated ≤ 3 days after COVID-19 symptom onset. This will be estimated without regard to adherence to randomized treatment.

2.1.2. Secondary Estimands

The estimand associated with the key secondary efficacy objective is the difference in proportions of patients experiencing COVID-19-related hospitalization or death from any cause through Day 28 in nonhospitalized adult patients with symptomatic COVID-19 who are at increased risk of progression to severe disease and who did not receive COVID-19 therapeutic mAb treatment. This will be estimated without regard to adherence to randomized treatment.

The estimand associated with the secondary efficacy objective regarding the duration and severity of signs and symptoms is the absolute difference in median time to sustained alleviation or resolution of symptoms for all nonhospitalized adult patients with COVID 19 who are at increased risk of progression to severe disease. This will be estimated irrespective of adherence to randomized treatment.

The hospitalization/death rate through Day 28 is considered the main clinical outcome measure and signs/symptom duration is considered key secondary for this study and so estimands for these measures are presented. Estimands for the other outcome measures that are considered supportive of the primary outcome measures and of the sign/symptoms duration and severity outcome measure are not presented.

2.2. Study Design

This Phase 2/3, randomized, double-blind, placebo-controlled study in approximately 2260 symptomatic participants with COVID-19 who are nonhospitalized will determine the efficacy, safety, and tolerability of PF-07321332/ritonavir compared with placebo. Eligible participants with a confirmed diagnosis of SARS-CoV-2 infection will be randomized (1:1) to receive PF-07321332 and ritonavir or placebo orally q12h for 5 days (10 doses total). Randomization will be stratified by geographic region and by whether participants have received/are expected to receive treatment with COVID-19 therapeutic mAbs based on the

site investigator's assessment at time of randomization. Throughout the study period, provision will be made to allow study visits to be conducted at a participant's home or at another nonclinic location approved by the investigator where possible when participants are unwilling or unable to attend a clinic visit.

[figure not shown]
The total study duration is up to 24 weeks and includes a screening period of no more than 48 hours, study intervention through Day 5 or Day 6, efficacy assessments through Day 28, a safety follow-up period through Day 34, and long-term follow up at Weeks 12 and 24.

An independent E-DMC will review unblinded data to ensure the safety of participants on an ongoing basis throughout the duration of the study, as specified in the E-DMC Charter. In addition to up to weekly reviews of safety, the E-DMC will review the following:

- Sentinel cohort safety review: The E-DMC will review unblinded safety data after approximately the first 60 participants have completed Day 10 of the study, at which point enrollment will be paused pending E-DMC review of the safety data. After review of the sentinel cohort, the frequency of safety reviews may be reduced subsequently based on E-DMC recommendations.
- Proof-of-concept assessment: The E-DMC will review viral load data when approximately 200 participants in the primary analysis set with evaluable data complete the Day 5 assessments. Enrollment will not be paused during review of these data but may be paused or stopped following E-DMC review.
- Formal interim analysis: A planned formal interim analysis for efficacy and futility with a sample size re-estimation will be done after approximately 45% of participants in the mITT analysis set complete the Day 28 assessments.

Subsequent to the planned interim analyses, there will be 2 analyses for reporting the results of this study. The primary analysis will be performed after all participants have completed the Day 34 visit. The follow-up analysis will be performed after all participants have completed the Week 24 visit. The study schematic is provided in Figure 1.

Figure 1. C4671005 Study Design

a. The baseline and scheming visits may be a combination or impersion and elementarie visits. b. The Day's visits hould be conducted in-person for the first 60 participants(sentine) cohort) and thereafter only if a PK sample (not using Tasso) is collected by an HCP or if ECG is required.

PFIZER CONFIDENTIAL
Page 13

2.3. Sample Size Determination

This study is designed to have 90% statistical power to show a difference of 3.5% in the proportion of participants hospitalized/dying that did not receive COVID-19 therapeutic mAb between the treatment arms (PF07321332/ritonavir versus placebo) and were treated \leq 3 days after COVID-19 symptom onset, using a 2-sided Type I error rate of 5%. Based on the BLAZE study², the proportion of hospitalization/death in the placebo arm is assumed to be 7%.

Using EAST (Version 6.5) for a 2 sample proportion test¹, the sample size needed to detect a 3.5% difference with 90% power at a 2-sided significance level of 5% was determined to be 1717 randomized participants. Enrollment of participants who at baseline had received or were expected to receive COVID-19 therapeutic mAb treatment is estimated to be approximately 20% of participants and limited/capped to 25% enrollment.

Enrollment of participants-that had COVID-19 symptom onset >3 days prior to randomization is expected to be approximately 25% and will be limited to approximately 1000 participants. Assuming a 5% dropout rate, the total sample size for this study will be approximately 3000 participants.

To allow for a 5% dropout rate, enrollment will be stopped after approximately 1717 participants are available for the primary analysis.

3. ENDPOINTS AND BASELINE VARIABLES: DEFINITIONS AND CONVENTIONS

3.1. Primary Endpoint

• Proportion of participants with COVID-19 related hospitalization or death from any cause through Day 28.

3.2. Secondary Endpoint(s)

- The first key secondary efficacy endpoint is the proportion of participants with COVID-19 related hospitalization or death due to any cause through Day 28 in the mITT1 analysis set.
- Incidence of treatment emergent adverse events (TEAEs).
- Incidence of SAEs and AEs leading to discontinuations.
- *Time (days) to sustained alleviation of all targeted signs/symptoms through Day 28.*
- Proportion of participants with severe signs/symptoms attributed to COVID-19 through Day 28.
- *Time (days) to sustained resolution of all targeted signs/symptoms through Day 28.*

- Duration of each targeted COVID-19 sign/symptom.
- Progression to a worsening status in 1 or more self reported COVID19 associated symptoms through Day 28.
- *Proportion of participants with a resting peripheral oxygen saturation* ≥95% *at Days 1 and 5.*
- Proportion of participants with death (all-cause) through Week 24.
- *PF-07321332 PK in plasma and whole blood (if feasible).*
- Viral titers measured via RT-PCR in nasal swabs over time.
- Number of COVID-19 related medical visits.
- Number of days in hospital and ICU stay in participants with COVID-19 related hospitalization.

3.4. Baseline Variables

For viral load data, baseline visit is set up according to study days of Day -2 to Day 1. Only results that are within 1 hour post start of dosing will be treated as Baseline data. Laboratory assessments Signs and Symptoms, Vital Signs and ECG: Baseline window will be Day -2 to Day 1, without any consideration to the time factor.

The following baseline variables will be used in efficacy analyses. See below a list of derived baseline variables based on baseline viral load data:

- Baseline viral load defined as: $<10^4$ copies/mL vs $\ge 10^4$ copies/mL.
- Baseline viral load defines as: $<10^7$ copies/mL vs $\ge 10^7$ copies/mL.
- Baseline serology status defined as positive or negative.

3.5. Stratification Variables

Randomization will be stratified by geographic region and whether participants had received or were expected to receive COVID-19 therapeutic mAb treatment (yes/no) based on the site investigator's assessment at the time of randomization. Randomization for the strata where participants had received or were expected to receive COVID-19 therapeutic mAb treatment will be capped at a maximum of 25% enrollment. Unless otherwise indicated analyses will include calculated values for quantitative stratification variables. Geographical region is defined as follows:

- US region: country of the United States, including Puerto Rico.
- Europe region: countries of Bulgaria, Czech Republic, Hungary, Netherlands, Poland, Spain, and Ukraine.
- Brazil region: country of Brazil.
- India region: country of India.
- Rest of the World region: countries of Argentina, Colombia, Japan, Malaysia, Mexico, Peru, Russian Federation, South Africa, Republic of Korea, Taiwan, Thailand, and Turkey.

If a region enrolled <10 participants, the region will be combined with the "rest f the word" region.

Baseline and stratification variables above defined will be applied to the analyses depending on the analysis population used:

- mITT analyses will include the following stratification variables: Baseline viral load, baseline serology status, geographic region.
- mITT1 analysis will include: Baseline viral load, baseline serology status, geographic region and symptom onset days to first dose date (≤3 days, >3 days).
- mITT2 analyses will include: Baseline viral load, baseline serology status, geographic region, received or were expected to receive mAb treatment (yes/no) and symptom onset days to first dose date (≤3 days, >3 days).

3.6. Safety Endpoints

The safety endpoints of this study are:

- Incidence of TEAEs.
- Incidence of SAEs and AEs leading to discontinuations.

Clinical Data Interchange Standards Consortium (CDISC) and Pfizer Standards (CaPS) will be used for the analysis of standard safety data.

3.6.1. Adverse Events

An adverse event (AE) is any untoward medical occurrence in a study participant administered a product or medical device; the event need not necessarily have a causal relationship with the treatment or usage. An adverse event is considered a Treatment-Emergent Adverse Event (TEAE) if the event started on or after the study medication start date and time.

PFIZER CONFIDENTIAL
Page 16

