## 2.3.1. Risk Assessment

Potential Risk of Clinical Significance	Summary of Data/Rationale for Risk	Mitigation Strategy
	Study Intervention(s) PF-07321332	
Emesis	Sporadic emesis was observed at ≥100 mg/kg/day of PF-07321332 in the 15-day NHP toxicology study.	AEs will be monitored and participants may receive antiemetics.
Hemodynamic and inflammatory effects	Low level inflammation (increase in fibrinogen) in 15-day NHP toxicology study and changes in platelets, globulin and albumin/globulin ratio and coagulation system (increase in PT and aPTT) in 14-day rat toxicology study.	In addition to vital signs and close observation for AEs, fibrinogen, platelets, D-dimer, PT and aPTT, albumin, and total protein will also be monitored. Refer to Section 8.3.8.
TSH elevations	TSH changes observed with the administration of	TSH and T4 (free) will be monitored.
	PF-07321332 during study C4671001	Refer to Section 8.3.8.
	Study Intervention(s): Ritonavir	
Gastrointestinal disturbances (including diarrhea, nausea, vomiting and abdominal pain)	Frequently reported adverse reaction in HIV-positive patients who are HIV-positive at 600 mg BID.	Lower dose of 100 mg twice daily is used in this study. There will be close observation of AEs. In addition to ongoing review of AEs by the sponsor, an E-DMC will review safety data as described in Section 10.1.5.1.
		Taking study intervention with food may improve tolerability.
Neurological disturbances (eg, paresthesia, including oral paresthesia, dysgeusia and	Frequently reported adverse reaction in patients who are HIV-positive at 600 mg BID.	Lower dose used in this study. There will be close observation of AEs.
dizziness)		In addition to ongoing review of AEs by the sponsor, an E-DMC will review safety data as described in Section 10.1.5.1.
Rash (most commonly reported as erythematous and maculopapular, followed by pruritic)	Frequently reported adverse reaction in patients who are HIV-positive at 600 mg BID.	Lower dose used in this study. There will be close observation of AEs and monitoring through targeted physical exams. If needed therapeutic interventions per SoC may be provided.

Potential Risk of Clinical Significance	Summary of Data/Rationale for Risk	Mitigation Strategy

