Fatigue/Asthenia	Frequently reported adverse reaction in patients who are HIV-positive at 600 mg BID.	Lower dose used in this study. There will be close observation of AEs. Fatigue (low energy or tiredness) will be assessed through collection of daily signs and symptoms and will also be assessed through targeted physical examinations when performed during the study visits.

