### Type of Participant and Disease Characteristics:

2. Confirmed SARS-CoV-2 infection as determined by RT-PCR in any specimen collected within 5 days prior to randomization.

Note: RT-PCR is the preferred method; however, with evolving approaches to confirmation of SARS-CoV-2 infection, other molecular or antigen tests that detect viral RNA or protein are allowed. The test result must be available to confirm eligibility. Participants may be enrolled based on positive results of a rapid SARS-CoV-2 antigen test performed at screening.

- 3. Initial onset of signs/symptoms attributable to COVID-19 within 5 days prior to the day of randomization and at least 1 of the specified signs/symptoms attributable to COVID-19 present on the day of randomization (see Appendix 9 for criteria).
- 4. Has at least 1 characteristic or underlying medical condition associated with an increased risk of developing severe illness from COVID-19 including:
  - $\geq 60$  years of age;
  - BMI >25;
  - Current smoker (cigarette smoking within the past 30 days) and history of at least 100 lifetime cigarettes;
  - Immunosuppressive disease (eg, bone marrow or organ transplantation or primary immune deficiencies) OR prolonged use of immune-weakening medications:
    - Has received corticosteroids equivalent to prednisone ≥20 mg daily for at least 14 consecutive days within 30 days prior to study entry.
    - Has received treatment with biologics (eg, infliximab, ustekinumab), immunomodulators (eg, methotrexate, 6MP, azathioprine) or cancer chemotherapy within 90 days prior to study entry.
    - $\circ~$  HIV infection with CD4 cell count  ${<}200~mm^3$  and a viral load less than 400 copies/mL
  - Chronic lung disease (if asthma, requires daily prescribed therapy);
  - Known diagnosis of hypertension;
  - CVD, defined as history of any of the following: myocardial infarction, stroke, TIA, HF, angina with prescribed nitroglycerin, CABG, PCI, carotid endarterectomy, and aortic bypass;
  - Type 1 or Type 2 diabetes mellitus;
  - CKD provided the participant does not meet Exclusion Criterion 5;
  - Sickle cell disease;

- Neurodevelopmental disorders (eg, cerebral palsy, Down's syndrome) or other conditions that confer medical complexity (eg, genetic or metabolic syndromes and severe congenital anomalies);

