### 8.3.1. Time Period and Frequency for Collecting AE and SAE Information

The time period for actively eliciting and collecting AEs and SAEs ("active collection period") for each participant begins from the time the participant provides informed consent, which is obtained before the participant's participation in the study (ie, before undergoing any study related procedure and/or receiving study intervention), through and including a minimum of 28 calendar days, except as indicated below, after the last administration of the study intervention.

Follow up by the investigator continues throughout and after the active collection period and until the AE or SAE or its sequelae resolve or stabilize at a level acceptable to the investigator.

For participants who are screen failures, the active collection period ends when screen failure status is determined.

If the participant withdraws from the study and also withdraws consent for the collection of future information, the active collection period ends when consent is withdrawn.

If a participant permanently discontinues or temporarily discontinues study intervention because of an AE or SAE, the AE or SAE must be recorded on the CRF and the SAE reported using the CT SAE Report Form.

Investigators are not obligated to actively seek information on AEs or SAEs after the participant has concluded study participation. However, if the investigator learns of any SAE, including a death, at any time after a participant has completed the study, and he/she considers the event to be reasonably related to the study intervention, the investigator must promptly report the SAE to Pfizer using the CT SAE Report Form.

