## **Events** Meeting the AE Definition

- Any abnormal laboratory test results (hematology, clinical chemistry, or urinalysis) or other safety assessments (eg, ECG, radiological scans, vital sign measurements), including those that worsen from baseline, considered clinically significant in the medical and scientific judgment of the investigator. Any abnormal laboratory test results that meet any of the conditions below must be recorded as an AE:
  - Is associated with accompanying symptoms.
  - Requires additional diagnostic testing or medical/surgical intervention.
  - Leads to a change in study dosing (outside of any protocol-specified dose adjustments) or discontinuation from the study, significant additional concomitant drug treatment, or other therapy.
- Exacerbation of a chronic or intermittent preexisting condition, including either an increase in frequency and/or intensity of the condition.
- New condition detected or diagnosed after study intervention administration, even though it may have been present before the start of the study.
- Signs, symptoms, or the clinical sequelae of a suspected drug-drug interaction.
- Signs, symptoms, or the clinical sequelae of a suspected overdose of either study intervention or a concomitant medication. Overdose per se will not be reported as an AE or SAE unless it is an intentional overdose taken with possible suicidal/self-harming intent. Such overdoses should be reported regardless of sequelae.

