## Follow-Up of AEs and SAEs

- The investigator is obligated to perform or arrange for the conduct of supplemental measurements and/or evaluations, as medically indicated or as requested by the sponsor, to elucidate the nature and/or causality of the AE or SAE as fully as possible. This may include additional laboratory tests or investigations, histopathological examinations, or consultation with other healthcare providers.
- If a participant dies during participation in the study or during a recognized follow-up period, the investigator will provide Pfizer Safety with a copy of any postmortem findings, including histopathology.
- New or updated information will be recorded in the originally submitted documents.
- The investigator will submit any updated SAE data to the sponsor within 24 hours of receipt of the information.

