6.6.1. Adverse Events

All adverse events will be coded according to the Medical Dictionary for Regulatory Activities (MedDRA) and will be summarized by treatment group within SAS population. Only TEAE summaries to AEs that started on or prior to Day 34 will be summarized. A list of pre-specified AESIs is provided in Appendix 4.

PFIZER CONFIDENTIAL
Page 30

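### SAP 3.6.1 classes TEAEs by start date and time alone, so a pre-dose AE that worsens on treatment is not counted; separately, diary fatigue has no readable by-arm analysis through Day 28

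*SAP*

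**What the plan says.** **The TEAE rule.** SAP 3.6.1 makes an AE treatment-emergent "if the event started on or after the study medication start date and time". SAP 6.2.2 and 6.6.1 add no severity clause. SAP 6.6.1 adds a second limit based on start date: "Only TEAE summaries to AEs that started on or prior to Day 34 will be summarized".

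**What the protocol records as an AE.** Protocol 10.3.1 includes "Exacerbation of a chronic or intermittent preexisting condition, including either an increase in frequency and/or intensity of the condition". It also includes a condition first found after dosing that may have been there earlier. It leaves out expected signs and symptoms of the disease under study unless they exceed what would be expected for that participant. Under Protocol 8.3.1, active collection "for each participant begins from the time the participant provides informed consent", so an AE can have a pre-dose start.

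**Symptoms at entry.** Inclusion criterion 3 requires "at least 1 of the specified signs/symptoms attributable to COVID-19 present on the day of randomization".

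**Fatigue.** Protocol 2.3.1 lists fatigue/asthenia under ritonavir. Its mitigation column says: "Fatigue (low energy or tiredness) will be assessed through collection of daily signs and symptoms", together with targeted physical examination. Protocol Table 2 and SAP Appendix 5 mark fatigue as an entry symptom and a daily diary item, but not as a targeted symptom for analysis.

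**The concern.** The protocol foresees AEs whose onset precedes dosing and which matter because they get worse. The SAP then sorts AEs by onset alone. In a trial where everyone is symptomatic at entry, worsening of an existing complaint is a foreseeable form of drug intolerance. TEAE incidence is the secondary endpoint meant to show it.

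Fatigue deserves separate attention. The protocol's stated safeguard for this risk is the diary, yet the SAP's diary analyses through Day 28 use targeted symptoms only. A by-arm view of fatigue in that period therefore has to come from AE records. At stake is the completeness of the safety description. No primary or key secondary efficacy result is touched.

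**Working it through.** No arithmetic in the plan bears on this point, so the check sets the texts side by side.

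**1. Which AEs does the start-date rule lose?**

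| Case | Counted as TEAE under SAP 3.6.1? |
|---|---|
| Pre-dose COVID-19 symptom that stays within what is expected | Not an AE at all (Protocol 10.3.1) |
| Pre-dose symptom that exceeds expectation after dosing, entered as an AE dated at the worsening | Yes |
| Same, but the AE is dated back to symptom onset | No |
| AE recorded between consent and first dose that worsens after dosing, original record updated | No |
| Same, but the worsening is entered as a new AE | Yes |

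The loss is confined to the third and fourth rows. No text in the two documents tells sites which dating convention to use.

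**2. How large can it be?** Let s be the share of worsened AEs whose condition began before first dose, and d the share of those that keep a pre-dose start date. The share missing from TEAE incidence is s × d. The documents give neither input. As illustrations only:
- d = 0 gives 0% for any s.
- s = 0.50 and d = 0.50 gives 0.50 × 0.50 = 25%.
- s = 0.75 and d = 1 gives 0.75 × 1 = 75%.

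These values are assumptions, neither bounds nor estimates. The texts suggest that few AEs qualify. The AE exclusion for expected disease symptoms applies first. The schedule of activities puts screening at Day -1 to Day 1, often under 24 hours, and Protocol 4.1 caps it at 48 hours.

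**3. Which symptoms are exposed?** Protocol Table 2 marks 12 entry symptoms, 14 diary items and 11 targeted symptoms. The untargeted diary items number 14 − 11 = 3: fatigue, loss of smell and loss of taste. Four entry symptoms are also named ritonavir risks in Protocol 2.3.1: fatigue, and three from the row that reads "Gastrointestinal disturbances (including diarrhea, nausea, vomiting and abdominal pain". Diarrhea, nausea and vomiting are targeted, so SAP 6.2.5 tabulates each by arm from the diary. Fatigue is the only one of the four that is not.

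**4. Is diary fatigue reported elsewhere through Day 28?** The SAP analyses of alleviation and resolution (6.2.4), severe symptoms (6.2.5), duration (6.2.6) and worsening (6.2.7) are all limited to targeted symptoms. All symptoms, fatigue included, are summarized by arm only at Weeks 12 and 24, from a telemedicine interview. Protocol 9.3.6.2 mentions a by-arm physical examination summary. However, Protocol 8.2.3 treats those findings as source data that generally need not be reported, and the SAP plans no such table.

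**5. Does the SAP have a worsening concept already?** Yes. SAP 6.2.7 derives worsening relative to baseline for targeted symptoms. The safety definition has no counterpart.

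**The case against.** The strongest reply is that the rule seldom bites. Ordinary COVID-19 fatigue before dosing is not an AE, so usually no pre-dose AE record exists to keep an early date. If fatigue exceeds expectation only on treatment, the AE is naturally opened then, and the exacerbation itself can be read as the event that started. This largely stands and is why the affected set is probably small. It does not cover an AE opened between consent and dosing, or one dated back to symptom onset.

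Conventions may also sit in documents not available here. Protocol 10.1.7 refers to a separate CRF completion document, and SAP 3.6 cites sponsor reporting standards. Either might deal with worsening. If so, SAP 3.6.1 as written disagrees with them and should be aligned.

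The SAP 6.6.1 sentence is awkward and may be only a Day 34 cut-off, and SAP 6.2.3 does not restrict SAEs or AEs leading to discontinuation to TEAEs. A serious or treatment-ending worsening could therefore still appear there. The risk table also reports these ritonavir effects at 600 mg BID and notes that the trial dose is lower. Both remarks stand and reduce the weight of the point.

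A reader might infer that the rule directly contradicts Protocol 8.3.1 and 10.3.3. It does not. Section 8.3.1 sets when collection begins. The line in 10.3.3, "New or updated information will be recorded in the originally submitted documents", concerns follow-up documentation. It neither governs onset dating nor forbids a new record.

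**Conclusion.** Two limited points hold.

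First, SAP 3.6.1 would leave out of TEAE incidence an AE that began before first dose, or is dated to pre-dose symptom onset, and worsened after dosing, although the protocol counts the worsening as an AE. The set is probably small and its size cannot be computed. The result rests on two assumptions: that some sites keep the earlier date, and that the unseen CRF guidance and sponsor standards do not already settle the matter.

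Second, and independently, the SAP does not report by arm through Day 28 the fatigue data on which the protocol's risk mitigation relies. This is limited to what can be read, since parts of the SAP are redacted.

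A reader might go further and conclude that a substantial share of drug-related fatigue will vanish from the safety tables. The documents give no rates to support that, and the AE exclusion for expected symptoms would filter much fatigue before the start-date rule applied. For the same reason the TEAE clause alone would not make fatigue visible, so the diary row is needed as well.

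**What to change.** 1. Amend SAP 3.6.1 so that an AE is treatment-emergent if it started on or after first dose, or started before it and increased in severity afterwards. This works only where a severity change is recorded. Records with a pre-dose date and no recorded change cannot be recovered.
2. Add fatigue, with denominators, to the by-arm symptom presence and severity table of SAP 6.2.5 through Day 28. Label it descriptive and net of any antiviral effect: a difference between arms cannot isolate fatigue caused by the drug.

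**Cost.** One sentence and one table row, using data already collected. Some natural COVID-19 worsening will also count, so background TEAE rates rise slightly in both arms. The existing AE exclusion for expected disease symptoms stays in place and limits this.
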